##### **Secondary endpoints:**

- Baseline and post-intervention secondary outcome data on cardiometabolic markers (adiposity, pulse, and blood pressure) will be assessed online via self-report and include: changes in weight, pulse, and blood pressure (systolic and diastolic).
- Baseline, post-intervention, and 1-month post-intervention changes on psychological resilience and psychological distress will be assessed through an online survey:
  - Psychological resilience: shift-and-persist (Chen et al scale), mindfulness (FFMQ-15), psychological flexibility (Acceptance and Action Questionnaire - version 2 (AAQ-2)).
  - Psychological distress: depression symptoms (CESD-10), PTSD symptoms (PCL-2), anxiety symptoms (GAD-7), and perceived stress (PSS-4)
  - Health behaviors: emotional eating (TFEQ) and reward-based eating (RBD scale).
  - self-reported height, weight, and blood pressure

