## 2. Objectives

1. To evaluate the feasibility and acceptability of a 4-week mindfulness program among young women in Puerto Rico with elevated stress
2. To explore changes in psychological resilience, psychological distress, health behaviors, and cardiometabolic markers (blood pressure, pulse, weight, and waist circumference).

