#### **5. Study Intervention/Design**

This is a one-arm intervention study that will explore if a 4-week MBSR program is feasible and acceptable among young women in Puerto Rico with elevated stress. The intervention consists of 4 weekly virtual sessions and daily mindfulness exercises at home (between 5-16min of duration each, according to participant's availability). The participants will also complete three study assessments: baseline, post-intervention, and 1-month post-intervention. All study measures at all time points will be done online through questionnaires to be filled out by participants.

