#### **6. Procedures Involved**

Interested individuals who contact the study (via email or phone/text) for more information and/or provide their contact information through the Google Forms survey (see Google Forms survey document), will be contacted via phone, text or email by our research staff to set up a screening call

---

**Protocol Title:** Shift-and-persist and cardiometabolic markers among women in Puerto Rico: a pilot of a mindfulness-based trial

---

(described in detail in the Recruitment and Inclusion and Exclusion Criteria sections). All interested individuals will provide verbal consent prior to screening. A maximum of 10 attempts will be done to contact interested participants for scheduling a screening call.

Eligible individuals will receive the REDCap link (via email or text, according to the participant's preference) leading to the electronic informed consent after confirming eligibility by a research staff. The study personnel will describe the study protocol, discuss the informed consent, and answer any questions. Individuals will then fill out the electronic consent form and will be given access to the online baseline questionnaire (email or text). Study staff will also fill out the contact information form upon completion of consent (see Contact information form), where data on the participant's email, phone number, address and at least 2 emergency contacts will be collected. The survey is meant to be completed by participants on their own, but study staff will be available via phone or email if any question arises. This approach is currently being used in the PR-OUTLOOK study, a study of young adults in Puerto Rico. The PI of the study has also conducted online surveys filled by participants in Puerto Rico during the pandemic (as part of other studies) and got good response rates.

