provided and up to 10 reminders (via email, text or call) will be sent out to complete the assessment. The link to this last assessment will be sent out 1-month after completion of the intervention, but at least 3 weeks after the post-intervention assessment.

A weekly reminder will be sent out (the day prior to the session, via text and email) to remind participants to join the weekly Zoom call. Up to 10 reminders (on each occasion, via text, email or call) will be sent out to participants to complete the baseline, post-intervention, and 1mo post-intervention online questionnaire.

All gift cards will be electronic gift cards and the information will be sent out to participants via email or text.

Participants will be notified that all experiences shared during intervention sessions are considered confidential and should not be discussed outside of the group.

The following table shows the different measures being collected at the different time points (also see questionnaire/instruments provided for data collection at baseline, post-intervention, and 1mo post-intervention).

Timepoint	Baseline	Post intervention	1mo post intervention
Socio-demographics			
Age	X		
Gender	X		
Health insurance	X		
Education	X		
Income	X		
Municipality	X		
Food security	X		
SNAP	X		
Marital Status	X		
Perceived income	X		
Employment	X		
Mental health			
Depression (CESD-10)	X	X	X
PTSD (PCL-2)	X	X	X
Anxiety (GAD)	X	X	X
Perceived stress (PSS-4)	NA-included in screening	X	X
Resilience			
SP (Chen et al)	X	X	X
Mindfulness (FFMG-15)	X	X	X
Psychological flexibility (AAQ2)	X	X	X
Health behaviors			

PA (WHI)	X	X	
Perceived sleep qual	X	X	
Diet screener (Mattei et al)	X	X	
Emotional eating (TFEQ R18 V2)	X	X	X
Reward based eating (Reward based eating scale (RED))	X	X	X
Smoking	X	X	
e-cigarettes	X	X	
Clinical characteristics			
Self-reported diagnosis	X		
Medical care for mental health	X		
Medications for mental health	X		
Anthropometrics			
Self-reported blood pressure	X	X	X
Self-reported weight	X	X	X
Self-reported height	x	x	x
Self-reported pulse	x	x	x
Intervention			
Satisfaction		X	
Stress management		X	
Group and instructor environment		x	
Exercise that helped the most		X	X
Exercise most often practiced		X	X
# sessions attended		x	
Frequency of daily practice and duration		X	X
Overall feedback		X	

We have delineated a suicide prevention protocol as explained in section #19 of this document.

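### Must the protocol tie self-reported blood pressure, pulse and weight to a dated reading near each assessment?

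*Combined protocol and SAP*

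**What the plan says.** Section 2 (Objectives) makes change in "cardiometabolic markers (blood pressure, pulse, weight, and waist circumference") an exploratory objective. Section 4 says the markers are self-reported online and lists "changes in weight, pulse, and blood pressure (systolic and diastolic") at baseline and post-intervention. Its last sub-bullet, under the heading that adds the 1-month assessment, lists "self-reported height, weight, and blood pressure".

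Section 5 sets the mode: "All study measures at all time points will be done online through questionnaires to be filled out by participants". Section 6 adds "The survey is meant to be completed by participants on their own", with staff reachable by phone or email for questions. The Section 6 schedule labels the rows simply "Self-reported blood pressure" and "Self-reported pulse" (weight and height likewise) and marks all of them at all three assessments. For the items themselves the reader is sent elsewhere: "also see questionnaire/instruments provided for data collection at baseline, post-intervention, and 1mo post-intervention".

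Section 18 analyses change in each secondary outcome with mixed linear models adjusted for baseline covariates.

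**The concern.** A symptom scale can be answered from introspection. Blood pressure and pulse cannot be known without a measurement. The protocol provides no device and no visit, Section 21 describes everything as online, and Section 23 rules out review of medical records, so no stated source could check an entry. The assessments are close together: a 4-week programme, then about a month. A woman might enter the same remembered clinic value twice, and the model would read that as no change. She might also guess, perhaps favourably after a stress-reduction course.

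At stake is how to interpret the reported changes in markers that appear in the study title. Exact repeats would also shrink the spread, so the estimate would look more precise while lying further from the truth.

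**Working it through.** **1. What the text settles.** I looked for a reading date, look-back window, device or source in every section that mentions these measures or the timing of assessments. None is stated. Two phrases come close but do not serve. Section 19 refers to real-time entry, which concerns when data reach REDCap. The minimum of 3 weeks in Section 6 governs when the last survey link is sent. The protocol body is therefore silent. The item wording is in instruments I have not seen, so it cannot be said whether the trial itself is silent.

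**2. What depends on these outcomes.** The primary endpoints in Section 4 are recruitment, retention, adherence and satisfaction. The sample of 30 (3 waves × about 10 = 30) rests on a pilot rule of thumb of at least 12 per group, with no effect size, SD, alpha or power. Neither uses the markers.

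**3. How large an error could be.** The plan gives no figure to reproduce, so all inputs here are assumed. Let *f* be the share of women with a stale or guessed pair, *d* the true mean change and *s* the mean recorded change among the stale pairs. Then

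observed mean = (1 − f)·d + f·s.

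With d = −4 mmHg:

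| f | s = 0 (exact repeats) | s = −8 | s = +4 | s = −4 |
|---|---|---|---|---|
| 0.1 | −3.6 | −4.4 | −3.2 | −4.0 |
| 0.2 | −3.2 | −4.8 | −2.4 | −4.0 |
| 0.5 | −2.0 | −6.0 | 0.0 | −4.0 |

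For example, f = 0.2 and s = −8 gives 0.8 × (−4) + 0.2 × (−8) = −4.8. The result runs from dilution through no effect to exaggeration, according to an *s* that nobody knows.

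For exact repeats (s = 0) and an SD of 10 mmHg among fresh pairs, the variance of recorded change is (1 − f)·100 + f(1 − f)·16. At f = 0.5 this is 50 + 4 = 54. With n = 30, the half-width of a one-sample 95% t interval and its simulated coverage of d are:

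| f | half-width, mmHg | coverage |
|---|---|---|
| 0 | 3.73 | 95% |
| 0.1 | 3.57 | 94% |
| 0.2 | 3.39 | 92% |
| 0.5 | 2.74 | 65% |

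Serious loss needs about half the women to repeat a value exactly. The t interval is simpler than the planned mixed model.

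**4. What the data can show without new items.** Repeats can be counted in REDCap. Under assumed change SDs, a fresh blood pressure pair repeats both numbers 0.2% of the time when recorded to 1 mmHg, 4% when rounded to 5 and 15% when rounded to 10. These take systolic and diastolic as independent; with a correlation of 0.7 they become about 0.3%, 6% and 19%. A cluster of identical pairs would therefore stand out unless rounding is coarse. The check is weaker for pulse (5%, 23% and 43% at rounding to 1, 5 and 10) and for weight (8–17% to 1 lb, 36–65% to 5 lb), and it cannot detect guesses.

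**5. Time points.**

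| Marker | Section 4, first bullet | Section 4, last sub-bullet | Section 6 schedule |
|---|---|---|---|
| Blood pressure, weight | baseline, post | adds 1 month | all three |
| Pulse | baseline, post | not listed | all three |

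The schedule collects all three markers at 1 month, so no data are lost under either reading. Waist circumference is named in Sections 2 and 19 but is in neither the endpoint list nor the schedule. That is also a wording mismatch, separate from the timing of readings.

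**The case for a change.** The best case for a change is that it is cheap and cannot be made later. A reading date that was not requested is hard to recover, the repeat check misses guesses, and a feasibility pilot is a natural place to learn how many women can supply two dated, measured values. A date and a source question for each marker would need no devices or staff.

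Much of this stands. The protocol body is silent, and checking the data afterwards is only a partial substitute. It is reasonable for the team to look at the items and confirm that they ask for a current reading.

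It does not amount to a fault in the plan. The argument depends on wording that has not been seen. Self-report is openly declared as the method. A date and a source for three markers would add six questions per assessment, 18 over three, to a survey whose completion is itself part of what the pilot studies. An analysis limited to measured readings would use a self-selected subset. With an SD of 10 mmHg its half-width would be 7.2 at n = 10 and 10.5 at n = 6, against 3.7 for all 30, so it could only supplement the planned analysis.

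**Conclusion.** No change to the plan is called for. This is detail that normally sits in the questionnaire, and the protocol points to the questionnaire. No stated rule has been shown to give a wrong result. Any bias would fall on exploratory outcomes in a one-arm pilot of 30 and would leave the primary endpoints untouched. Its direction is unknown. Its size rests wholly on assumed values of *f*, *d*, *s* and the SD: slight for exact repeats at f of 0.1 or less, and serious for exact repeats only near f = 0.5.

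Analysts can handle the rest in the ordinary way: describe the markers as self-reported, count identical blood pressure pairs, and interpret the changes cautiously. The uneven time points and the stray mention of waist circumference are editorial, and the Section 6 schedule already shows what will be collected. The conclusion would be worth revisiting only if the questionnaires proved silent on when a reading was taken and these changes were later used to plan a larger trial.

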#### **5. Study Intervention/Design**

This is a one-arm intervention study that will explore if a 4-week MBSR program is feasible and acceptable among young women in Puerto Rico with elevated stress. The intervention consists of 4 weekly virtual sessions and daily mindfulness exercises at home (between 5-16min of duration each, according to participant's availability). The participants will also complete three study assessments: baseline, post-intervention, and 1-month post-intervention. All study measures at all time points will be done online through questionnaires to be filled out by participants.

#### **6. Procedures Involved**

Interested individuals who contact the study (via email or phone/text) for more information and/or provide their contact information through the Google Forms survey (see Google Forms survey document), will be contacted via phone, text or email by our research staff to set up a screening call

---

**Protocol Title:** Shift-and-persist and cardiometabolic markers among women in Puerto Rico: a pilot of a mindfulness-based trial

---

(described in detail in the Recruitment and Inclusion and Exclusion Criteria sections). All interested individuals will provide verbal consent prior to screening. A maximum of 10 attempts will be done to contact interested participants for scheduling a screening call.

Eligible individuals will receive the REDCap link (via email or text, according to the participant's preference) leading to the electronic informed consent after confirming eligibility by a research staff. The study personnel will describe the study protocol, discuss the informed consent, and answer any questions. Individuals will then fill out the electronic consent form and will be given access to the online baseline questionnaire (email or text). Study staff will also fill out the contact information form upon completion of consent (see Contact information form), where data on the participant's email, phone number, address and at least 2 emergency contacts will be collected. The survey is meant to be completed by participants on their own, but study staff will be available via phone or email if any question arises. This approach is currently being used in the PR-OUTLOOK study, a study of young adults in Puerto Rico. The PI of the study has also conducted online surveys filled by participants in Puerto Rico during the pandemic (as part of other studies) and got good response rates.

Individuals will receive the 4-week tailored intervention in groups (3 waves of approximately 10 participants each; these may be stacked, overlapping, or following completion of each group, according to the instructor's availability). All weekly sessions will be delivered via Zoom. My team and I have the expertise and are equipped to recruit and implement the telephone-delivered program given our prior virtual studies in Puerto Rico and US Latinxs during the COVID-19 pandemic. Once in the intervention, participants will join one session weekly (on Zoom) and will receive access to online audio files, which are the daily practice exercises to be done at home.

Each session has a duration of 1hr (except the first session which is longer due to introductions and describing the program's logistics and expectations). The sessions follow a brief check-in, lecture on the week's topic, and guided practice. For the audio files, for each exercise, participants will have the opportunity to select a short version of the practice (5-8min) or a longer version (12-16min) according to their daily availability. The following table outlines the 4-week MBSR session topics and daily home-practice exercises.

Session	Topic	Home exercise
Week 1	Orientation; Introduction to stress and its consequences	Awareness of breathing
Week 2	Awareness of sensations	Body Scan
Week 3	Thoughts are not facts	Awareness of thoughts
Week 4	Recap; Mindful eating, mindful walking	Awareness of eating

After completion of the intervention, participants are encouraged to continue doing the mindful daily exercises at home by accessing the audio files. Following the last session, participants will be given access to the online questionnaire for the post-intervention measures, which will include the Contact information form. Research staff will have 10 attempts (via email, text or call) to contact participants and remind them to fill out the questionnaire.

1mo post-intervention, participants will be contacted to complete the third and final assessment, an online questionnaire, which will also include the Contact Information Form. The link to the survey will be

---

**Protocol Title:** Shift-and-persist and cardiometabolic markers among women in Puerto Rico: a pilot of a mindfulness-based trial

provided and up to 10 reminders (via email, text or call) will be sent out to complete the assessment. The link to this last assessment will be sent out 1-month after completion of the intervention, but at least 3 weeks after the post-intervention assessment.

A weekly reminder will be sent out (the day prior to the session, via text and email) to remind participants to join the weekly Zoom call. Up to 10 reminders (on each occasion, via text, email or call) will be sent out to participants to complete the baseline, post-intervention, and 1mo post-intervention online questionnaire.

All gift cards will be electronic gift cards and the information will be sent out to participants via email or text.

Participants will be notified that all experiences shared during intervention sessions are considered confidential and should not be discussed outside of the group.

The following table shows the different measures being collected at the different time points (also see questionnaire/instruments provided for data collection at baseline, post-intervention, and 1mo post-intervention).

Timepoint	Baseline	Post intervention	1mo post intervention
Socio-demographics			
Age	X		
Gender	X		
Health insurance	X		
Education	X		
Income	X		
Municipality	X		
Food security	X		
SNAP	X		
Marital Status	X		
Perceived income	X		
Employment	X		
Mental health			
Depression (CESD-10)	X	X	X
PTSD (PCL-2)	X	X	X
Anxiety (GAD)	X	X	X
Perceived stress (PSS-4)	NA-included in screening	X	X
Resilience			
SP (Chen et al)	X	X	X
Mindfulness (FFMG-15)	X	X	X
Psychological flexibility (AAQ2)	X	X	X
Health behaviors			

PA (WHI)	X	X	
Perceived sleep qual	X	X	
Diet screener (Mattei et al)	X	X	
Emotional eating (TFEQ R18 V2)	X	X	X
Reward based eating (Reward based eating scale (RED))	X	X	X
Smoking	X	X	
e-cigarettes	X	X	
Clinical characteristics			
Self-reported diagnosis	X		
Medical care for mental health	X		
Medications for mental health	X		
Anthropometrics			
Self-reported blood pressure	X	X	X
Self-reported weight	X	X	X
Self-reported height	x	x	x
Self-reported pulse	x	x	x
Intervention			
Satisfaction		X	
Stress management		X	
Group and instructor environment		x	
Exercise that helped the most		X	X
Exercise most often practiced		X	X
# sessions attended		x	
Frequency of daily practice and duration		X	X
Overall feedback		X	

We have delineated a suicide prevention protocol as explained in section #19 of this document.

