## 1. Study Summary

Study Title	Shift-and-persist and cardiometabolic markers among women in Puerto Rico: a pilot of a mindfulness-based trial.
Study Design	One arm behavioral intervention
Primary Objective	To evaluate the feasibility and acceptability of a 4-week mindfulness program among young women in Puerto Rico with elevated stress
Secondary Objective(s)	To explore changes in psychological resilience, health behaviors, stress, and cardiometabolic markers
Research Intervention(s)/Interactions	3 study assessments (baseline, post-intervention, 1mo post-intervention)  4-week intervention (1 weekly virtual session)
Study Population	Young women residing in Puerto Rico (18-29y) with elevated stress
Sample Size	30
Study Duration for individual participants	2-4 months
Study Specific Abbreviations/ Definitions	MBSR: mindfulness-based stress reduction
Funding Source (if any)	Emory BIRCWH program

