## 10. Inclusion and Exclusion Criteria

### *Inclusion criteria*

- Reporting female sex at birth
- Not identifying as a man, trans man, or trans woman.
- Between the ages of 18-29 years
- Individuals residing in Puerto Rico
- Spanish speaking
- Currently not pregnant
- Elevated stress (defined as a score  $\geq 6$  in the Perceived Stress Scale (PSS-4))
- Willing to undergo research activities (focus group discussions).

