## 13. Recruitment Methods

Spanish-speaking women between 18-29 y will be recruited through flyers posted/disseminated through social media (e.g., Instagram, Facebook, Twitter) and social pages/accounts. These pages are those from mentors and collaborators outside of Emory University given that Emory pages do not currently have the reach to the population in Puerto Rico. These pages include collaborators that have already worked with the PR in other studies and include: CienciaPR, PR-CEAL, Puerto Rico Public Health Trust, Ciencia en Tus Manos, Estudio PROSPECT, among others. Recruitment flyers will also be disseminated through newsletters and email blasts at academic organizations (not including Emory) including the University of Puerto Rico, Ponce Health Sciences University, and San Juan Bautista School of Medicine, among others.

---

**Protocol Title:** Shift-and-persist and cardiometabolic markers among women in Puerto Rico: a pilot of a mindfulness-based trial

---

Additionally, the printed flyer will be distributed (in-person) at community events, health fairs and billboards.

The study flyer includes a study email where interested individuals can contact the study staff for more information and to assess eligibility. The flyer also includes a QR code and its respective link to a Google Forms survey where interested individuals can enter their contact information. Specifically, the Google Forms survey only asks for 1) First and Last Name, 2) phone number and 3) email.

Interested individuals will provide verbal consent (see Verbal Consent document). Afterwards, individuals will be screened for eligibility via phone (see Screening Questionnaire). Data will be directly entered in the database (REDCap or excel). Screening questions include age, sex, gender, PSS-4, PHQ-9, history of cognitive and psychiatric conditions, prior participation in an 8-week MBR program, currently pregnant, and access to internet/phone:

- 1- Female sex at birth
- 2- Not identifying as man, trans man, or trans woman
- 3- Self-reported age = needs to be between 18-29y
- 4- Currently residing in Puerto Rico
- 5- PSS-4 score  $\geq 6$
- 6- PHQ-9 scores  $\leq 15$
- 7- A negative response to item #9 ("Thoughts that you would be better off dead, or thoughts of hurting yourself in some way?)
- 8- No self-reported history of cognitive and psychiatric conditions
- 9- Affirmative response on access to internet/phone
- 10- No prior participation in an 8-week MBSR program

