## **18. Data Analysis, Management and Confidentiality**

Baseline descriptive statistics will include frequencies for categorical variables and means and standard deviations for continuous ones. Recruitment, adherence, retention, and satisfaction will be calculated for the total sample and will be explored by sociodemographic characteristics (i.e., age, income, employment, and education level). Changes in each secondary outcome will be evaluated using mixed

---

linear regression models controlling baseline covariates. We will conduct exploratory analyses among those with high levels of adherence (vs. low). STATA version 17 and SAS version 9.4 will be used.

Sample size considerations are driven by publications regarding pilot study planning. A minimum of 12 individuals per group is recommended for feasibility and precision around the estimates. Other MBCT pilot studies have included a similar sample size. This sample size suits the goals of this study to assess feasibility.

All study staff will be up to date with the Collaborative Institutional Training Initiative (CITI) Human Subjects trainings and will be trained for all protocols, including informed consent and data collection. The research team will maintain all responses and documents confidential. Individuals participating in the intervention will be informed that information disclosed within the intervention sessions is considered confidential and should not be repeated outside of the group. The data collected will only be used for research purposes. Only the research team will have access to the files. The electronic consent form and eligibility criteria will remain stored electronically. Identifiable information will not be shared to anyone and will be kept in a password-protected computer at Emory University and in the PI's OneDrive/SharePoint files.

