## **22. Informed Consent**

Verbal consent, via phone, will be obtained for all interested individuals prior to conducting the study screening questionnaire and after the staff describes the screening process (see Verbal Consent document). Informed consent will be obtained immediately after assessing eligibility of a study participant. Individuals will receive the REDCap link that leads to the electronic consent form. Consent will occur via phone call after the staff discusses the study and consent process. If the individual agrees to participate, they will provide an electronic signature. If technical difficulties arise with participants providing an electronic signature, a check on the “Yes” box following the statement “I consent to participate in the study” will suffice.

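### Baseline perceived stress is the phone-screening PSS-4 that had to reach 6 for entry, so regression to the mean alone is expected to produce a fall in this one-arm study

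*Combined protocol and SAP*

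**What the plan says.** In the section 6 table of measures by time point, the perceived stress row reads "NA-included in screening" at baseline and has an X at post-intervention and at 1 month. It is the only repeated scale without a baseline X; CESD-10, PCL-2 and GAD-7, listed in the same block, all have one.

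The screening score also decides entry. Section 10 requires "Elevated stress (defined as a score" of 6 or more on the PSS-4), and section 13 has the scale asked and scored during the phone screening.

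Two other sections describe something different. Section 4 lists the PSS-4 under psychological distress and says: "Baseline, post-intervention, and 1-month post-intervention changes on psychological resilience and psychological distress will be assessed through an online survey". Section 5 says: "All study measures at all time points will be done online through questionnaires to be filled out by participants".

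Stress is part of the secondary objective in section 1: "To explore changes in psychological resilience, health behaviors, stress, and cardiometabolic markers". For the analysis, section 18 says "Changes in each secondary outcome will be evaluated using mixed" linear regression models with baseline covariates. Section 5 describes a one-arm study. Regression to the mean is not mentioned.

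**The concern.** If the table is followed, one score both selects the women and serves as time 0. A PSS-4 score varies from week to week, so women whose score happened to be high on the day of the call are over-represented among those enrolled. Their next score is expected to be lower without any intervention. Adjusting for covariates does not remove this, because there is no comparison group in which the same fall could be seen.

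The mode of administration also changes for this outcome alone, from a staff member on the phone to self-completion online. The direction of that effect is unknown.

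Perceived stress is what the programme targets. Its estimated change would carry a component towards apparent benefit that has nothing to do with the programme, and section 8 expects the results to be published and summarised for participants.

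**Working it through.** The plan has no figure to reproduce: section 18 justifies the sample of 30 by pilot-study guidance, with no effect size, SD or alpha.

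**Inputs from the documents.** Entry at PSS-4 ≥ 6 (sections 10 and 13); 30 women (section 12); one arm (section 5). In the earlier focus-group study with the same criteria, 18 of 41 women screened were eligible (section 25): 18/41 = 44%. Those 18 met every criterion, so 44% is a floor for the share passing the PSS-4 criterion alone.

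**Assumed inputs.** SD 3; retest correlation r from 0.5 to 0.8; population mean set so that 44% to 90% pass the cut; no programme effect; two-sided 5% test (the protocol sets no alpha).

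**Formula.** For an approximately normal integer score, the expected fall is

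(1 − r) × SD × φ(c) / [1 − Φ(c)], with c = (5.5 − mean)/SD.

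**Middle case** (mean 6, r = 0.6):
- c = (5.5 − 6)/3 = −0.167; φ(c) = 0.393; 1 − Φ(c) = 0.566, so 57% pass.
- Excess of the selected mean over the population mean: 3 × 0.393/0.566 = 2.08 points.
- Expected fall: 0.4 × 2.08 = 0.83 points.

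**Ends of the range:**
- Mean 5.05 (44% pass), r = 0.5: c = 0.15; 0.5 × 3 × 0.394/0.440 = 1.34 points.
- Mean 9.35 (90% pass), r = 0.8: c = −1.283; 0.2 × 3 × 0.175/0.900 = 0.12 points.

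**Simulation** with scores rounded to integers from 0 to 16 and a paired t-test. A true null would give a significant decrease in 2.5% of trials.

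| Mean (share passing) | r | Mean change | Significant decrease, n=30 | n=24 |
|---|---|---|---|---|
| 5.05 (44%) | 0.5 | −1.37 | 75% | 64% |
| 5.05 (44%) | 0.8 | −0.57 | 36% | 29% |
| 6 (57%) | 0.6 | −0.85 | 42% | 35% |
| 8 (80%) | 0.8 | −0.22 | 9% | 8% |
| 9.35 (90%) | 0.5 | −0.30 | 8% | 7% |
| 9.35 (90%) | 0.8 | −0.12 | 5% | 5% |

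The 24 pairs allow for 6 of the 30 women being lost (an assumption). With SD 2.5 or 3.5 in the middle case, the change is −0.70 or −1.01.

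**Mixed model.** A random-intercept model with three time points, n = 30 and the middle case gives −0.83 at post-intervention (43% significant) and −0.82 at 1 month (42%). The planned type of model therefore does not remove the artefact.

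**Re-measuring time 0.** If the new baseline correlates with the screening score at q, the expected residual fall is (q − r) × 2.08. With r = 0.6:
- q = 0.6: 0; in the mixed model −0.03 at post-intervention (2.7% significant).
- q = 0.7: 0.1 × 2.08 = 0.21.
- q = 0.8: 0.2 × 2.08 = 0.42 (simulated 0.41).
- q = 0.9: 0.3 × 2.08 = 0.62 (simulated 0.63).

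Timing therefore matters. Section 22 says "Informed consent will be obtained immediately after assessing eligibility of a study participant", and section 13 opens the baseline questionnaire straight after consent. A PSS-4 asked at that moment would share much of the screening score's transient error.

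**The case against.** The strongest reply is about weight. The primary objective is feasibility and acceptability, the PSS-4 is one of many exploratory scales, and the protocol sets no efficacy hypothesis or alpha. No one-arm change can be attributed to the programme whichever baseline is used. All of that is right. It limits the consequence, but it does not justify building an avoidable component into the estimate.

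The size is also open to challenge. The 44% case means that no woman in the earlier study failed any criterion other than the PSS-4, and the 57% case needs 0.44/0.57 = 77% of those passing the PSS-4 to clear everything else. If 55% clear the rest, 0.44/0.55 = 80% pass the PSS-4, and the fall is 0.22 to 0.44 points for r of 0.8 to 0.6. The figure 18/41 is itself imprecise (exact 95% CI 28% to 60%). The middle case is therefore an illustration and not a best estimate.

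The calculation omits the PHQ-9 exclusion applied in the same call. One check, assuming correlation 0.6 with the PSS-4, left the fall nearly unchanged (0.65 with and without it at r = 0.7). Stronger assumptions brought the 0.85 down to 0.55–0.79. The sign did not change.

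The mode change could offset or add to the fall, so only the regression component has a known direction.

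Finally, section 19 says that screening and the online survey together collect distress data. That fits the table and suggests the cell is deliberate, with sections 4 and 5 loosely worded. If so, the bias applies as described. If a separate online baseline is in fact taken, the table is wrong and the bias is smaller, by an amount that depends on timing. The text needs correcting either way.

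**Conclusion.** The concern holds and should be fixed before the first session, because a time-0 score cannot be recovered afterwards. For any retest correlation below 1, following the table gives an expected fall in PSS-4 from selection alone. Its size cannot be derived from the documents. With SD 3, r of 0.5 to 0.8 and 44% to 90% of women passing the cut, it is 0.1 to 1.4 points, and an illustrative test would call it a significant decrease in 5% to 75% of no-effect trials with 30 pairs. If most screened women already score 6 or more, the effect is near the bottom of that range. The primary endpoints are unaffected, and CESD-10, PCL-2 and GAD-7 have their own baseline.

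**What to change.** - Ask the four PSS-4 items in an online self-completed assessment in the week before session 1, separate from the screening call, and close it when session 1 starts.
- Use that score as time 0 in the mixed model. Keep the screening score for eligibility only; a woman who re-scores below 6 stays in.
- Replace the table cell with an X and this timing, so that it agrees with sections 4 and 5.
- State in the report that, without a control arm, remaining regression to the mean and natural decline cannot be separated from a programme effect.

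**Cost.** Four items and one table cell. Women who complete the baseline questionnaire right after consent need one short extra REDCap link, which can accompany the reminder already planned for the day before the session (section 6). The section 9 timeline puts recruitment and baseline in the month before each wave's sessions, so the separation fits. The sections that describe three assessments (1, 5 and 9) need a line to cover the extra link. For these women the PSS-4 will have a later time 0 than the other distress scales. Women who do not open the link will have no time-0 PSS-4, and their number should be reported.

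Asking the items in the existing baseline questionnaire is simpler and still better than the current plan, but it may leave more of the artefact in place.
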